6.1.4 Progression-free Survival

Progression-free survival (PFS) is the time from study drug administration until disease progression or death. The disease assessment by the RECIST V1.1 criteria occurs at Screening, months 1, 3, 6, 9, 12, 18 and 24.

PFS is defined as the interval between the date of first infusion of and the date of PD or death, whichever is first reported.

PFS (days) =

Date of Progression – Date of 1st Infusion + 1

The following Kaplan-Meier (KM) estimates will be provided:

- 25th, 50th (i.e., median) and 75th KM percentiles with 95% CIs
- Number and percent of subjects censored/not censored

KM estimates of the proportion of subjects event-free at: 3, 6, 12, 18, and 24 months (note: not all estimates may be provided for interim analyses)

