6.6 Efficacy assessments: Radiological Assessment of Tumor Response

The tumor response assessment should be performed at the following time points:

- At Screening:
 - The investigator is encouraged to obtain the screening tumor scan as close as possible to the start of treatment within 28 days of C1D1.
- Within 7 days before the start of treatment on C3D1 and every other cycle thereafter (i.e. Between D23 and D28 of the cycle). The original schedule needs to be maintained even if there is a delay in dosing.
- Within 7 days of the EoT Visit (**only** if the previous tumor scan has been performed >4 weeks before the EoT Visit)

The investigator and the radiologist should carefully consider if the increase from baseline in tumor size could be “pseudoprogression” due to the tumor flare induced by the study drug(s).

Unscheduled tumor response assessment by FDG-PET-CT (or CT/MRI, where applicable) may be ordered at the investigator’s discretion.

Efficacy of the study drugs (tumor response) will be assessed by the scan of all anatomic regions involved with the measurable disease. Positron emission tomography-computed tomography should be used in subjects with FDG-avid tumor histology. Computed tomography or MRI should be used in subjects with tumor histology of low or variable FDG avidity. Diagnostic quality CT should be collected for all subjects at baseline, whenever possible.

Tumor response in subjects with FDG-avid tumor histology will be determined using the 5-point scale (5PS) according to the Lugano Classification for Lymphoma ([Cheson 2014](#)) adjusted according to LYRIC (lymphoma response to immunomodulatory therapy criteria) ([Cheson 2016](#)). An overview of NHL response criteria for FDG avid and non-avid NHL is presented in [Appendix 3](#).

The same technique (e.g. slice thickness, field of view) should be used for all scans during the study treatment period. Preferably, all scans should be interpreted by the same investigator during the study whenever possible. Scans must meet the SOC for imaging of lesions in the respective organ system(s).

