7.9 Efficacy analyses

The statistical analysis of efficacy variables will be performed on the safety population.

Tumor assessment will be performed by the FDG-PET-CT scan in subjects with FDG-avid NHL histology along with CT or MRI to capture measurements, wherever possible, and by the CT or MRI scan in subjects with low or variable FDG avidity. The investigator at each site will determine the ORR at each time point based on the radiologist's measurement of all evaluable lesions.

The investigator at each site will determine the objective tumor response (OR) using the 5PS per the Lugano Classification for Lymphoma ([Cheson 2014](#)) adjusted according to LYRIC (lymphoma response to immunomodulatory therapy criteria) ([Cheson 2016](#)). An overview of LYRIC is presented in [Appendix 3](#). The BORR of all time points will be reported. Subjects

who experience disease progression before undergoing the first tumor assessment will be added to the disease progression stratum. The BORR will be descriptively summarized by the treatment group/cohort; the exact 95% confidence intervals will also be produced.

The ORR representing clinically significant clinical benefit in this study will comprise the Lugano Score 1, 2 or 3, or the CR or PR. All subjects achieving clinically significant clinical benefit according to both response criteria will be included in the analysis of the DOR. DOR is defined as the time from the first documented complete or partial response to the actual date of disease progression or death before progression. The PFS will be defined as the time from the start of treatment with MT-3724 on C1D1 to the date of disease progression or death from any cause. Subjects who have not progressed or died at the time of data base lock will be censored at the date of their last tumor assessment. The DOR will be descriptively summarized by the treatment group/cohort; the exact 95% confidence intervals will also be produced.

The DCR will be defined as the percent of subjects with objective response of CR, PR or stable disease (SD, defined as SD for 6 months or longer). The DCR will be analyzed using similar methods as the ORR. Further details will be provided in the SAP.

A detailed description of analysis methods will be provided in the SAP to be completed before the EoT Visit in the last subject.

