4. CHANGES TO PLANNED ANALYSIS

The statistical methods described in this SAP take precedence over the protocol. Additional exploratory efficacy endpoints have been added.

- [REDACTED]
- [REDACTED]

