7.2 Secondary Analysis

A secondary analysis of efficacy to evaluate response to MT-3724 in combination with lenalidomide will be performed in this trial. The efficacy parameters of interest are objective response rate (ORR), best objective response rate (BORR), and duration of response (DOR). All efficacy summaries will be based on the safety population.

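### SAP 6.1.4 bases PFS on RECIST 1.1 and a scan calendar that conflict with the protocol, and its formula leaves out the death date that its own definition includes

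*SAP*

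**What the plan says.** **SAP 6.1.4 (PFS).** The criteria and calendar are given in one sentence: "The disease assessment by the RECIST V1.1 criteria occurs at Screening, months 1, 3, 6, 9, 12, 18 and 24". The opening sentence of the section counts death as an event, and the definition does so again: "PFS is defined as the interval between the date of first infusion of and the date of PD or death, whichever is first reported". The computation line is "Date of Progression – Date of 1st Infusion + 1". The section asks for Kaplan-Meier quartiles, event-free proportions, and the number and percentage of subjects censored. It does not say who is censored, or when.

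**SAP 6.1.1 (ORR).** Response is judged on the Lugano five-point scale with the LYRIC adjustment.

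**Protocol 7.9.** The investigator "will determine the objective tumor response (OR) using the 5PS per the Lugano Classification for Lymphoma", adjusted for LYRIC; Appendix 3 holds the criteria. PFS runs from the start of MT-3724 on C1D1 "to the date of disease progression or death from any cause". Subjects with neither event at database lock are censored at their last tumor assessment.

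**Protocol 6.6 and 3.5.** Scans are due at screening; then "Within 7 days before the start of treatment on C3D1 and every other cycle thereafter"; then around the EoT Visit if the previous scan is more than 4 weeks old. In long-term follow-up, radiology is taken from medical records for subjects with CR, PR or SD until progression, death or new anticancer treatment.

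**SAP section 4.** "The statistical methods described in this SAP take precedence over the protocol". Its visible text does not list the PFS criteria or calendar as a change.

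**The concern.** RECIST 1.1 appears in SAP 6.1.4 and nowhere in the protocol. Taken at its word, the SAP would judge ORR by lymphoma criteria and PFS by a different system, in the same subjects and on the same scans. The month calendar describes visits at which the protocol mostly schedules no scan. The formula needs a progression date, so a subject who dies without documented progression has nothing to enter, although the definition printed with it counts that death. Protocol 7.9 leaves detailed methods to the SAP, and the SAP claims precedence, so neither document settles the matter for the programmer. At stake is whether the reported PFS is reproducible and means what protocol 7.9 says it means.

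**Working it through.** Neither document gives a power calculation or event count for PFS, so there is no planned figure to reproduce. Three checks were made.

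**1. Calendar**

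Inputs: 28-day cycles; scans on D23-D28 of cycles 2, 4, 6 and so on (protocol 6.6); C1D1 as day 1; 30.4375 days per month. The window in cycle c is day (c − 1) × 28 + 23 to day (c − 1) × 28 + 28. For c = 2, 4 and 6 this gives days 51-56, 107-112 and 163-168. SAP month m falls on day m × 30.4375 + 1.

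| SAP month | Day | Nearest protocol window | Gap (days) |
|---|---|---|---|
| 1 | 31.4 | 51-56 | 20 |
| 3 | 92.3 | 107-112 | 15 |
| 6 | 183.6 | 163-168 | 16 |
| 9 | 274.9 | 275-280 | about 0 |
| 12 | 366.2 | 387-392 | 21 |
| 18 | 548.9 | 555-560 | 6 |
| 24 | 731.5 | 723-728 | 4 |

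Month 9 coincides with a window by chance. For a subject still on treatment, 6 post-baseline scans are due by month 12 under the protocol against 5 under the SAP. By month 24 the counts are 13 and 7.

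**2. Criteria and event, side by side**

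| Element | Protocol | SAP |
|---|---|---|
| Response criteria | Lugano/LYRIC | Lugano/LYRIC for ORR; RECIST 1.1 for PFS |
| PFS event in words | Progression or death | Progression or death |
| PFS formula | None printed | Progression date only |
| PFS censoring | Last tumor assessment | Not stated, but counts requested |
| LYRIC indeterminate response | In Appendix 3; no PFS status given | No PFS status given |

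The last row matters in practice. On CT, an SPD increase above 50% in the first 12 weeks (12 × 7 = 84 days) is an indeterminate response under Appendix 3. The first scheduled scan, on days 51-56, falls inside that period.

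**3. What omitting the death date could do (illustration only)**

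Assumptions: constant hazards; true median PFS of 3.7 months, the lenalidomide-rituximab figure quoted in protocol 1.3.1; and s, the share of first events that are deaths without documented progression. The documents give no value for s.

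*If those deaths are censored when they occur:* the progression hazard is (1 − s) times the total, so the median is 3.7/(1 − s) and 6-month PFS is 0.5^(6(1 − s)/3.7).

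| s | Median (months) | 6-month PFS |
|---|---|---|
| 0 (deaths counted) | 3.7 | 32.5% |
| 5% | 3.7/0.95 = 3.9 | 34.4% |
| 10% | 3.7/0.90 = 4.1 | 36.4% |
| 20% | 3.7/0.80 = 4.6 | 40.7% |
| 30% | 3.7/0.70 = 5.3 | 45.5% |

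*If those subjects have a missing value and drop out:* SAP 5.4 says missing data are not imputed. Under constant hazards with complete follow-up, the time of the first event does not depend on its type. The median among subjects who progress first therefore stays at 3.7 months.

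The same formula thus gives different results depending on a choice that the SAP does not make.

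**The case against.** The strongest reply is that nobody would run the section literally. Its prose counts death twice, in line with the protocol. SAP precedence covers those sentences as much as the formula. Sites are told to assess by Lugano/LYRIC on the protocol schedule, and the SAP presents itself as detailing the protocol's analyses, so its silence on censoring need not displace protocol 7.9. PFS is also one of several secondary, descriptive endpoints in an unpowered study whose primary endpoints concern safety. No hypothesis test rests on it, and dose decisions rest on DLTs.

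Much of this stands, and it rules out several stronger readings that a reader might infer:

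- **That the SAP excludes deaths from PFS, or that the result would not be the protocol's endpoint.** Only the one-line formula omits death. This is an internal contradiction, not a settled exclusion.
- **That PFS would be biased upward by a known amount.** That requires an unstated decision to censor deaths and an assumed share of deaths.
- **That the month calendar also drives the DOR rule on missed evaluations.** SAP 6.1.3 cites no calendar, and SAP Appendix A is a placeholder for the protocol's schedule.
- **That no data exist for RECIST.** The protocol plans no RECIST assessments, but protocol 7.9 does collect CT or MRI measurements where possible.

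The reply does not remove the conflict itself. RECIST 1.1 and the month list are printed as the PFS method in the document that claims precedence, and the formula contradicts the definition beside it.

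**Conclusion.** The point holds in this form. SAP 6.1.4 conflicts with the protocol and with the SAP's own ORR section on response criteria, and with the protocol on scan timing. Its formula contradicts its own definition, and the censored counts it requests rest on no stated rule. Literally applied, the formula gives no PFS value for a death without documented progression.

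The direct discrepancies are certain because they are on the page: four of the seven SAP months lie 15 to 21 days from any protocol window, and 7 post-baseline assessments are listed by month 24 against 13 for a subject on treatment throughout. The scan counts do not apply after treatment ends. The numerical effect on PFS is not determined. The 4.1-5.3 month range depends on censoring the deaths, constant hazards, a 3.7-month median from another regimen, and death shares of 10-30% that the documents do not supply.

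The section should be corrected before database lock, although the consequence is limited to a secondary, descriptive endpoint.

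**What to change.** Rewrite SAP 6.1.4 as follows:

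1. Delete RECIST 1.1 and the month list. Define progression by Lugano/LYRIC as in protocol Appendix 3.
2. State the PFS status of a LYRIC indeterminate response, which neither document does now.
3. Refer to the protocol schedule in full: screening; within 7 days before C3D1 and every other cycle after that; EoT if the last scan was more than 4 weeks earlier; and follow-up radiology until progression, death or new anticancer treatment. A list of on-treatment scans alone would again misstate the protocol.
4. Set PFS (days) = min(date of PD, date of death) − date of first MT-3724 infusion + 1.
5. Censor subjects without an event at their last tumor assessment, as in protocol 7.9.

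Separately, add a Kaplan-Meier summary of OS. It is a protocol secondary endpoint, and the visible SAP contains no analysis of it. Protocol 7.9 gives no OS method either, so this is a distinct omission and the point above does not depend on it.

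The cost is SAP wording and programming, with no new data. PFS may read somewhat shorter than it would if deaths without progression were censored.

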7.3 Pharmacokinetic and Pharmacodynamic Analyses

MT-3724 serum concentration/time data from all eligible subjects will be subjected to noncompartmental analysis (NCA) using the software package Phoenix WinNonlin (Certera, Princeton NJ). PK parameters will be stratified by MT-3724 dose group and summary statistics will be generated. Exploratory analyses between PK and PD results as well as clinical responders will be conducted, as appropriate. Details will be provided in a separate analysis plan for this study objective.

7.4 Immunogenicity Analyses

Data for the ADA against MT-3724 will be obtained as titer, if the screening and confirmation assays are positive, while the data for the neutralizing antibodies (NA) against MT-3724 will be obtained as either positive or negative. The number and percent of subjects with a detectable ADA titer, and separately with a positive NA result, will be summarized by time point for each treatment group/cohort. The individual subject's immunogenicity results will be listed by time point for each subject by treatment group/cohort. Details of the immunogenicity analyses will be provided in a separate analysis plan for this study objective.

8. SAFETY ANALYSIS

All safety summaries will be conducted using the safety analysis set. No formal hypothesis testing will be performed to compare differences between dose levels.

8.1 Extent of Exposure

The total number of doses received, the expected total dose, the actual dose administered, and outcome of infusion will be summarized and presented. Information in the listing will include total dose of MT-3724 administered, start and stop times, outcome of infusion, and duration of interruption (if applicable).

8.2 Adverse Events

An adverse event (AE) is any untoward medical occurrence in a subject or clinical investigation subject who is administered study drug, whether or not the event is considered related to the investigational product. An AE is therefore any unfavorable and unintended sign (including an abnormal laboratory finding), symptom, or disease (new or exacerbated) temporally associated with the use of the study drug. Examples of AEs include but are not limited to:

- Abnormal test findings
- Clinically significant symptoms and signs
- Changes in PE
- Hypersensitivity
- Signs, symptoms, or the clinical sequelae of a suspected overdose of either investigational product or a concurrent medication

Any AE or SAE occurring after the subject provides informed consent and prior to receiving investigational product that is considered by the Investigator to be related to study procedures, will be reported.

8.2.1 Pre-treatment-emergent Adverse Events

Pre-treatment AEs include those aspects of the patient's medical history that were ongoing at consent, as well as the new or worsening AEs reported between the screening medical history and the start of treatment. These AEs will be assessed by verbal probes and from medical history. The pre-treatment AEs will be listed by subject but not summarized.

8.2.2 Treatment-emergent Adverse Events

A treatment-emergent adverse event (TEAE) is defined as any event not present prior to exposure of study drug or an event already present that worsens in either severity or frequency following exposure.

8.2.3 Adverse Event Severity

The CTCAE v.5.0 will be used for grading the severity of AEs. Every effort should be made to find the appropriate AE term and definition of severity in the CTCAE v.5.0. If the AE term chosen by the investigator is not listed in the CTCAE v.5.0, then the highest severity level on the scale in the following table will be assigned to the investigator's AE term.

Classification of Adverse Events by Severity Grade (CTCAE v.5.0)

Grade	Description
Grade 1 (mild)	An AE that is easily tolerated by the subject. It incurs only a minimum of discomfort and does not influence ordinary daily tasks.
Grade 2 (moderate)	An AE that is of sufficient severity to have a negative influence on ordinary daily tasks.
Grade 3 (severe)	An AE that effectively hinders ordinary daily tasks, often requiring intervention.
Grade 4 (life threatening or disabling)	An AE that puts the subject's life at risk.
Grade 5 (fatal)	Death related to an AE.

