6.3.3 Severity

Severity will be classified according to the criteria provided by CTCAE v5.0. If the AE is not listed in the CTCAE v5.0, then the highest severity level reached according to the scale in Table 8 will be assigned.

Table 8: Classification of Adverse Events by Severity

Grade	Definition
Grade 1 (mild)	An AE that is easily tolerated by the subject. It incurs only a minimum of discomfort and does not influence ordinary daily tasks.
Grade 2 (moderate)	An AE that is of sufficient severity to have a negative influence on ordinary daily tasks.
Grade 3 (severe)	An AE that effectively hinders ordinary daily tasks, often requiring intervention.
Grade 4 (life threatening or disabling)	An AE that puts the subject's life at risk.
Grade 5 (fatal)	Death related to an AE.

AE =adverse event

Every effort should be made to find the appropriate AE term and definitions of severity in the modified CTCAE v. 5.0.

Causality/Relatedness

Causality should be assessed separately for each study drug (MT-3724 and LEN) as detailed in the eCRF. If the investigator feels that the event cannot be firmly attributed to one of the study drugs, then the same assessment should be documented for each study drug. Causal relationship to protocol required procedure(s) should also be considered and reported accordingly in the eCRF.

The following should be considered when assessing causality:

- temporal associations between the agent and the event
- effect of de-challenge and/or re-challenge
- pre-existing risk factors
- a plausible mechanism
- concurrent illnesses.

The investigator will determine the causal relationship/relatedness to the study drug(s) according to the classification in Table 9.

Table 9 Classification of Adverse Events by Causality/Relationship to the Study Drug(s)

Causality/Relatedness	Definition
Definitely related	Follows a reasonable temporal sequence from drug administration, abates upon discontinuation of the drug (de-challenge), is confirmed by reappearance of the reaction on repeat exposure (re-challenge).
Probably related	Follows a reasonable temporal sequence from drug administration, abates upon discontinuation of the drug, cannot be reasonably explained by the known characteristics of the subject's clinical state.
Possibly related	Follows a reasonable temporal sequence from drug administration, could have been produced by the subject's clinical state or by other modes of therapy administered to the subject.

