7.3 Sample size justification

Approximately 64 subjects (i.e., 24 subjects in Part 1 and approximately 40 subjects in Part 2), as well as the appropriate number of replacements (if needed), will be enrolled and treated in this study. The actual number will depend on the number of dose cohorts needed to identify the MTD of MT-3724 in combination with LEN in Part 1.

No formal power calculation and sample size justification will be performed for this descriptive non-pivotal Phase 2a study. The proposed sample size is deemed sufficient for the adequate characterization of the study objectives and would be typical of the sample sizes of exploratory Phase 1b/2a studies with novel anti-cancer agents.

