8.2.6 Adverse Event Summaries

All AEs (serious and non serious) occurring after completion of the informed consent process and before the end of study, regardless of relationship to study drug, will be included and classified by system organ class (SOC) and preferred term (PT) using the Medical Dictionary for Regulatory Activities (MedDRA).

For treatment-emergent AEs (TEAEs), the following will be summarized and presented for the safety analysis set:

- i. An overall summary of TEAEs, which includes:
 - a. the number and percentage of subjects experiencing a TEAE
 - b. the number and percentage of subjects experiencing a TEAE by relationship to study medication (for each study medication)
 - c. the number and percentage of subjects experiencing a TEAE by greatest grade
 - d. the number and percentage of subjects experiencing a TEAE leading to study dose interruption
 - e. the number and percentage of subjects experiencing a TEAE leading to dose delay
 - f. the number and percentage of subjects experiencing a TEAE leading to dose reduction
 - g. the number and percentage of subjects experiencing a TEAE leading to study withdrawal
 - h. the number and percentage of subjects experiencing a TEAE of special interest (IRR, CRS, and CLS)
 - i. the number and percentage of subjects experiencing a treatment emergent SAE (TESAE)
- ii. the number and percentage of subjects experiencing a TEAE by SOC, PT
- iii. the number and percentage of subjects experiencing a TEAE by SOC, PT and relationship to study medication (for each study medication)
- iv. the number and percentage of subjects experiencing a TEAE by SOC, PT and greatest grade

- v. the number and percentage of subjects experiencing a TEAE leading to dose interruption by SOC and PT
- vi. the number and percentage of subjects experiencing a TEAE leading to dose delay by SOC and PT
- vii. the number and percentage of subjects experiencing a TEAE leading to dose reduction by SOC and PT
- viii. the number and percentage of subjects experiencing a TEAE leading to study withdrawal by SOC and PT
- ix. the number and percentage of subjects experiencing a TEAE of special interest by SOC and PT
- x. the number and percentage of subjects experiencing a TESAE leading to dose interruption by SOC and PT
- xi. the number and percentage of subjects experiencing a TESAE leading to dose delay by SOC and PT
- xii. the number and percentage of subjects experiencing a TESAE leading to dose reduction by SOC and PT

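### SAP 8.2.3 omits *reached* from the protocol's rule for grading AEs not listed in CTCAE, so read literally it makes every such event Grade 5 (fatal)

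*SAP*

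**What the plan says.** Both documents grade AE severity by CTCAE v5.0 and give a five-grade fallback table for events that CTCAE does not list. In both tables Grade 1 is mild and Grade 5 is fatal, defined as death related to the AE.

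The rules for using the table differ by one word:

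- Protocol 6.3.3: "then the highest severity level reached according to the scale in Table 8 will be assigned".
- SAP 8.2.3, for a term that CTCAE lacks: "then the highest severity level on the scale in the following table will be assigned". The SAP attaches this level to the term that the investigator chose.

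SAP section 4 adds: "The statistical methods described in this SAP take precedence over the protocol". The only change it legibly describes is the addition of exploratory efficacy endpoints. Its bullet items are redacted.

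The grade feeds two summaries in SAP 8.2.6: item i.c, "the number and percentage of subjects experiencing a TEAE by greatest grade", and item iv, "the number and percentage of subjects experiencing a TEAE by SOC, PT and greatest grade". The same section counts only the most severe episode (or the one most strongly related to study drug) when a subject has repeated episodes of a TEAE.

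**The concern.** The protocol rule depends on what happened to the subject: the event takes the worst level it attained. The SAP sentence no longer refers to the event's course. It names the top of the scale and attaches it to the AE term. The top of that scale is Grade 5, so a mild unlisted event would be recorded as a death related to an AE.

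Safety is the primary objective, and the greatest-grade tables are among its main displays. A programmer who follows SAP 8.2.3 to the letter produces false fatal grades. One who does not follow it departs from the SAP without a documented reason. SAP 5.1 requires each program to be checked against its specification, so the wording from which a specification would be written matters.

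**Working it through.** The plan gives no figure to reproduce. The check compares the texts, traces where the grade is used, and works out what one misgraded subject would do to a table.

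**1. The two rules applied to the same event**

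| Unlisted event | Protocol 6.3.3 | SAP 8.2.3, literal |
|---|---|---|
| Mild, easily tolerated | Grade 1 | Grade 5 |
| Interferes with daily tasks | Grade 2 | Grade 5 |
| Prevents daily tasks | Grade 3 | Grade 5 |
| Puts life at risk | Grade 4 | Grade 5 |
| Death related to the event | Grade 5 | Grade 5 |

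The rules agree only for an event that really was fatal. No other SAP section brings back the level reached.

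**2. Where the grade is used**

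- Affected: SAP 8.2.6 items i.c and iv, and the choice of most severe episode. The AE listing would show the same grade.
- Not affected: the number of subjects with any TEAE, incidence by SOC and PT, relatedness, and SAEs. SAP 8.2.5 bases seriousness on outcome or action, not on severity.
- Not affected: DLTs and the MTD. These follow Protocol 3.6.2, 3.6.3 and Appendix 4, with the sponsor making the determination. SAP 8.2.7 only counts the DLTs.

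**3. Effect of one affected subject**

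In a group of *n* subjects, one subject wrongly placed in the Grade 5 row adds 100/*n* percentage points. This assumes the subject had no genuine Grade 5 event.

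- Combined MTD group. Protocol 3.6.3 requires at least 6 subjects at the MTD in Part 1, and Protocol 3.7 allows up to 40 in Part 2. Protocol 7.2 and SAP section 5 provide for a combined summary. The documents do not state the combined size. Taking 6 + 40 = 46 as an assumption, 100/46 = 2.2 points. More MTD subjects from Part 1 would lower this, and fewer in Part 2 would raise it.
- Expansion cohort alone, if full: 100/40 = 2.5 points.
- Single escalation cohort. Protocol 3.6 starts with 3 or 4 subjects and expands to 6. This gives 100/3 = 33.3, 100/4 = 25.0 and 100/6 = 16.7 points.

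The total effect is the number of affected subjects times these figures. That number depends on how many reported terms are missing from CTCAE v5.0, which the documents do not give and which cannot be estimated from them.

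**The case against.** The best reply is that nobody would apply the sentence literally, and much of that reply stands.

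- **The table contradicts the literal reading.** Grade 5 is defined by death, which a non-fatal event cannot meet, and Grades 1 to 4 of the fallback table would never be used. The only reading that gives the table a purpose is the protocol's. This is good evidence of a slip, but it does not correct the sentence.
- **Grades are collected, not derived.** Protocol 6.3.2 has severity recorded from choices on the eCRF, and Protocol 6.3 has the investigator and the medical monitor's delegate review it for accuracy. SAP 5.1 calls for full source verification, and SAP 5.6 says that data derivations do not apply. No regrading step is programmed anywhere. A mild event would become fatal only if someone overrode a recorded and reviewed grade. This stands, and it makes actual misgrading unlikely.
- **The rule covers few events.** SAP 8.2.3 asks for every effort to find a CTCAE term first. This also stands.
- **Precedence is limited.** The SAP claims it for statistical methods, and grading an unlisted event is arguably a data-collection convention. SAP section 1 describes the SAP as detailing analyses the protocol specifies. The point is fair, but two documents would still give different rules for one variable in the safety tables.

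A reader might infer from the precedence clause that the sponsor meant to change the grading rule. The legible text of SAP section 4 does not support that. A reader might also infer that the study's fatal-event counts will be inflated, or that dose decisions are compromised. The documents support neither: no step regrades the data, and DLT and MTD decisions do not use this sentence.

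**Conclusion.** The sentence in SAP 8.2.3 is wrong as written and contradicts Protocol 6.3.3. It is almost certainly a drafting slip, and it should be corrected because it is the SAP's only rule for these events and it feeds grade tables for the primary objective.

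The consequence is conditional and narrow. Only if the rule were applied literally would the greatest-grade summaries and the most-severe-episode selection be distorted. Each affected subject would then add about 2 points to the Grade 5 row of a combined MTD group assumed to be about 46, or about 17 to 33 points in a cohort of 3 to 6. These are per-subject figures, not an estimate of the total effect, because the number of unlisted terms is unknown. No hypothesis test or power statement is involved. Protocol 7.3 says: "No formal power calculation and sample size justification will be performed for this descriptive non-pivotal Phase 2a study".

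It would go too far to say that the primary endpoint as a whole is affected. That endpoint is AE incidence including DLTs, and neither overall incidence nor the DLT count depends on this rule.

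**What to change.** In SAP 8.2.3, restore the protocol's rule: an AE whose term is not in CTCAE v5.0 takes the highest severity level *reached by the event* on the scale in the table that follows. This matches Protocol 6.3.3, with the SAP's own table in place of Table 8.

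At the same time, the title of the SAP table could drop its CTCAE v5.0 label, because the table is the fallback for terms outside CTCAE.

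The cost is a few words in the SAP. Data collection, sample size, dose decisions and study conduct do not change.
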